Normal and healthy volunteers (Group 1) and keratoconus patients (Group 2) will be recruited from patients of the contact lens service center at MEEI. The treating ophthalmologist at MEEI will initially introduce the study to the patient, and obtain a patient's permission to be contacted by study staff either (1) verbally during the course of providing medical care or (2) through the use of a recruitment letter.

If the patient agrees, the treating ophthalmologist at MEEI gives approval for their patient to be contacted for research purpose and obtains the patient's permission to be contacted by study staff.

In case a recruitment letter is used for initial contact of the patient, it will be mailed to the potential subjects at least a week prior to the potential subject's eye exam appointment. The subject will be encouraged to contact the research staff or their treating ophthalmologist by phone or email if they have any questions. If the treating ophthalmologist does not hear from the potential subject, they may follow up by phone.

Subject recruitment via email announcements or ad at PHC and MEEI

Normal and healthy volunteers can be recruited by PHC email announcement, the PHC Research website, the MEEI website, or through paper advertisements. Requirement for participation is either (a) having undergone a routine eye exam at MEEI within the last 12 months or (b) having a routine eye exam scheduled and completed at MEEI prior to study enrollment. Potential subjects who are interested in the study will contact the study staff. Eligibility will be determined and a study visit will be scheduled. The subject may be contacted by regular mail, electronic mail, or phone call to confirm date and time of scheduled study procedure as well as additional logistical information.

INCLUSION/EXCLUSION CRITERIA

Inclusion criteria

- Male or female subjects between the ages of 18 to 79 years
- Group 1 (N = 80): Healthy normal subjects with no significant eye disease and no significant refractive errors
- Group 2 (N = 10): Patients diagnosed with keratoconus

Exclusion criteria

- Volunteers with implanted intraocular lenses
- Volunteers with LASIK or any other eye surgery, and monocular volunteers
- Volunteers with restricted mobility, who cannot stand up, walk or sit still on a chair without a back
- Subjects who do not or cannot understand the instructions for imaging
- Subjects with diabetes, glaucoma family history
- Subjects who are pregnant and/or breastfeeding.

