VIII. STATISTICAL METHODS AND POWER ANALYSIS

Hypothesis: OCT Vibrography is able to detect sound induced resonance modes in the cornea and mode changes with age.

Analysis Plan: The relationship between the age of the subject (continuous explanatory variable) and the change in resonance mode (continuous outcome variable) will be investigated with linear regression.

Sample Size and Power for Group 1: Age-variation in sound induced resonance modes of the cornea has not been previously measured *in vivo*. As an approximation we considered the cornea to be a plate with a Young's Modulus of previously published data of corneas of human corneas with different ages [43]. Furthermore, we used previously published literature which deal with vibrations of circular plates in air [44] and water [45] to calculate resonance modes using above mentioned Youngs Modulus. We estimated the slope of variation in the cornea's (first) resonance mode with age to 5.6 Hz/year. If we measure an expected Gaussian distributed sample of healthy volunteers, we will need to measure 42 subjects to be able to reject the null hypothesis that this slope equals zero with probability (power) 0.9. The Type I error probability associated with this test of this null hypothesis is 0.05.

To account for any potential subjects lost in the study, we will have a total target enrollment of up to 80 subjects.

Sample Size and Power for Group 2: Currently, we do not know the effect size (difference in elastic modulus) required for power calculation. We are interested to test the performance of our device in detecting keratoconus over a small group of patients (N = 10).

IX. RISKS AND DISCOMFORTS

Risks and discomforts: OCT Vibrography

OCT is currently the standard-of-care for ophthalmology procedures and the device used for OCT Vibrography does not change the safety-related optical parameters relative to clinically deployed OCT imaging instruments. The OCT in use is a home built phase-sensitive OCT system which employs a polygon scanner swept laser in the spectral range from 1.23 to 1.34 μm with a typical sweep rate of 45 kHz and an optical power of 15 mW on the sample.

Direct contact with the cornea is routinely performed for intraocular pressure screening measurements by clinically-approved devices, including the Goldmann tonometer, TonoPen and iCare. It is a safe and well tolerated procedure provided the following criteria are met:

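### The powered age-slope analysis depends on how widely ages are spread, yet Group 1 has only age limits; soft age-band targets within the ceiling of 80 would improve precision cheaply

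*Combined protocol and SAP*

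**What the plan says.** Section VIII (Analysis Plan) specifies one powered analysis, a linear regression: "The relationship between the age of the subject (continuous explanatory variable) and the change in resonance mode (continuous outcome variable"). The Group 1 sample-size paragraph takes a slope of 5.6 Hz/year for the first resonance mode and a type I error of 0.05. It begins "If we measure an expected Gaussian distributed sample of healthy volunteers" and concludes that "we will need to measure 42 subjects to be able to reject the null hypothesis that this slope equals zero with probability (power) 0.9". To allow for losses, "we will have a total target enrollment of up to 80 subjects". No loss rate, age SD or residual SD is given.

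On who is enrolled, Section IV sets only limits: "Male or female subjects between the ages of 18 to 79 years". Healthy volunteers come from two routes. Some "will be recruited from patients of the contact lens service center at MEEI". For the other route, "Normal and healthy volunteers can be recruited by PHC email announcement, the PHC Research website, the MEEI website, or through paper advertisements". Section II asks for healthy people of differing ages but gives no distribution. Section V (Equitable Selection) adds nothing on age. No section contains an age band, quota or stratum.

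**The concern.** In a regression on age, subjects near the middle of the age range add little information about the slope, and subjects near the ends add most. A sample size for a slope therefore assumes a particular spread of ages. Here n is fixed, while the spread is left to whoever attends the clinic or answers an advertisement.

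The word Gaussian does not settle the matter. It could describe age or the outcome, and no SD comes with it. Writing the missing SDs into Section VIII would make 42 checkable, but it would not make the enrolled sample match them. Only a recruitment rule does that. Change with age is the study's stated hypothesis, so what is at stake is the precision of its main result.

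**Working it through.** **Inputs from the protocol.** Slope 5.6 Hz/year, alpha 0.05, power 0.9, n = 42 and ceiling 80 (Section VIII); ages 18 to 79 (Section IV).

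**Assumptions.** A two-sided test (sidedness is not stated), a straight line, constant residual SD and one value per subject. Three age distributions are compared:
- Six equal bands (18-29, 30-39, 40-49, 50-59, 60-69, 70-79): SD 17.58 years. A uniform spread gives almost the same, 61/√12 = 17.61.
- Gaussian centred at 48.5, nominal SD 61/4 = 15.25, truncated at 18 and 79: SD 13.41.
- The same with nominal SD 61/6 = 10.17: SD 10.03.

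**Formulas.** SE(slope) = residual SD / (age SD × √(n−1)). Power comes from the noncentral t with n−2 degrees of freedom and noncentrality d√(n−1), where d = slope × age SD / residual SD.

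**The plan's own figure.** 42 cannot be reproduced, because both SDs are missing. It can only be back-solved. Power 0.9 at n = 42 needs d = 0.519. With 5.6 Hz/year, residual SD = 5.6 × age SD / 0.519:
- age SD 10.03: 108 Hz
- age SD 13.41: 145 Hz
- age SD 17.58: 190 Hz

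The documents do not say which pair applies, if any.

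**Precision at equal n.** SE ratios against equal bands are 17.58/10.03 = 1.75 and 17.58/13.41 = 1.31. Narrower samples do worse: ages spread evenly over 20 to 50 have SD 30/√12 = 8.66, a ratio of 17.61/8.66 = 2.03 against a uniform 18-79 sample.

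**Case A: 42 was sized on an even spread.** The clustered samples then have d = 0.519 × 10.03/17.58 = 0.296, or 0.519 × 13.41/17.58 = 0.396.

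| Age SD (years) | Power, n = 42 | Power, n = 80 | Evaluable n for 0.90 |
|---|---|---|---|
| 10.0 | 0.46 | 0.74 | 123 |
| 13.4 | 0.70 | 0.93 | 70 |

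Using n in place of n−1 moves the last column to 125 and 71. Simulation that lets the achieved spread vary gives 0.45 and 0.68 at n = 42, and 0.73 and 0.93 at n = 80.

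**Case B: 42 was sized on the clustered ages.** Power is 0.90 at 42, as stated, and 0.995 if all 80 are evaluable. An even spread would reach 0.90 with about 16 subjects (sized on SD 10.0) or 26 (sized on SD 13.4).

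**Detectable slope with equal bands, power 0.90.** For n = 42, 0.519/17.58 = 0.0295, about 0.030 residual SD per year. For n = 60, d = 0.429 and 0.429/17.58 = 0.024.

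**The case against.** The strongest reply is that the power losses in case A need a baseline the protocol does not state. The only distributional word in Section VIII is Gaussian. If it refers to age, 42 already allows for clustering and nothing is lost. Even if 42 was sized on SD 13.4 and enrolment came in at SD 10.0, 80 evaluable subjects would still give about 0.93. This stands, and it is why the losses are given only as conditional.

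The ceiling of 80 also absorbs much. In case A it covers SD 13.4 provided at least 70 are evaluable, but it does not cover SD 10.0. Against that, the protocol offers the margin for lost subjects, and Section VII drops anyone whose measurements fail after 20 attempts.

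The age SDs are assumptions, which is also true. A reader might infer that the plan confines the age SD to between 10 and 17.6 years. It does not: limits of 18 to 79 allow less than 10, and up to 30.5 with subjects only at the two ends.

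Age spread is half of the gap, since the residual SD is missing too. The fix therefore asks for both.

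Lastly, rigid band caps could do harm. Suppose ages 60-69 yield five subjects and 70-79 none (an assumption). A hard cap of 13 per band then stops at n = 57 (4 × 13 + 5) with power 0.83, against 0.92 if enrolment runs on to 80 in the same pattern. With nobody over 59 the figures are 0.69 and 0.87. Band targets should be soft.

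**Conclusion.** This is a cheap improvement rather than an error. The plan's only powered analysis depends on age spread, and no section sets or targets that spread. At equal n, the clustered samples considered here widen the slope's standard error by 31% or 75% relative to equal bands, conditional on the assumed Gaussian ages.

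A reader might infer that the study is underpowered, or that 42 or 0.9 is wrong. The documents support neither. Both SDs are absent, so 42 can be neither confirmed nor refuted, and the low power values apply only if it was sized on an even spread. What holds under either reading of Gaussian is that a wider, more even spread of ages than these clustered samples gives a more precise slope from the same number of subjects.

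**What to change.** 1. **Section IV.** Recruit Group 1 towards six age bands: 18-29, 30-39, 40-49, 50-59, 60-69 and 70-79. Aim for at least 7 evaluable per band (7 × 6 = 42), with about 13 enrolled per band as a soft target (13 × 6 = 78, within the ceiling of 80). Give priority to under-filled bands and replace failed acquisitions from the same band where possible. Before enrolment closes, release unfilled places to other bands, preferably the oldest and youngest available, so that total n is not reduced.
2. **Section VIII.** State the age SD and the residual SD in Hz behind 42 and 5.6 Hz/year, and say what is assumed Gaussian. Add that with equal bands (age SD about 17.6 years, two-sided 0.05) power is 90% for a slope of about 0.030 residual SD per year with 42 evaluable subjects, and 0.024 with 60.
3. **Reporting.** Give the achieved age SD and the slope with its 95% confidence interval.

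The cost is one recruitment rule and a few sentences, with no added subjects, visits or procedures. The downside is time. The oldest bands may fill slowly, because Section IV excludes "Volunteers with implanted intraocular lenses" and anyone with previous eye surgery. The documents give no figure for how many older volunteers this removes.
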